## LIST OF ABBREVIATIONS AND RELEVANT DEFINITIONS

AKI	Acute Kidney Injury
APACHE	Acute Physiology And Chronic Health Evaluation
ARDS	Acute Respiratory Distress Syndrome
COVID-19	Coronavirus disease 2019
DP	Driving Pressure
EtCO 2	End-tidal Carbon Dioxide
FiO 2	Fraction of inspired Oxygen
HCO 3 	Bicarbonate
IBW	Ideal Body Weight
ICU	Intensive Care Unit
I:E ratio	Inspiratory : Expiratory ratio
NIV	Non-invasive ventilation
P max	Maximum airway pressure
P peak	Peak pressure
P plateau	Plateau pressure
PaO 2	Partial Arterial Pressure of Oxygen
PaCO 2	Partial Arterial Pressure of Carbon Dioxide
PBW	Predicted Body Weight
PEEP	Positive End-Expiratory Pressure
RR	Respiratory Rate
RR SET	Set Respiratory Rate
SaO 2	Saturation of Arterial Oxygen
SAPS	Simplified Acute Physiology Score
SARS-CoV-2	Severe acute respiratory coronavirus-2
SD	Standard Deviation
SOFA	Sequential Organ Failure Assessment Score
SpO 2	Saturation of peripheral Oxygen
V T	Tidal Volume
VILI	Ventilator induced lung injury
VTE	Expiratory tidal volume

## **SUMMARY**

### **Rationale**

The novel coronavirus disease (COVID–19) pandemic is rapidly expanding across the world, with over 60.000 new cases each day as of late March 2020. Healthcare workers are struggling to provide the best care for patients with proven or suspected COVID–19. Approaches for clinical care vary widely between and within countries and new insights are acquired rapidly. This includes the way invasive ventilation is applied.

### **Objective**

To determine and compare invasive ventilation settings and parameters in COVID–19 patients in the Netherlands, and to determine associations with clinical outcomes.

### **Hypotheses**

Invasive ventilation settings and parameters vary between intensive care units (ICUs) in hospitals in the Netherlands; certain ventilator settings have an independent association with duration of ventilation in COVID–19 patients.

### **Study design**

National, multicenter, service review.

### **Study population**

Invasively ventilated patients with proven or suspected COVID–19.

### **Methods**

In every patient, granular ventilator settings and parameters are collected from start of invasive ventilation for up to 72 hours. Patients will be followed up until ICU and hospital discharge, and until day 90.

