### **Study endpoints**

Main ventilator settings (including tidal volume, airway pressures, oxygen fraction and respiratory rate) (primary) and parameters (blood gas results); use of rescue therapies (including prone positioning); use of sedatives, vasopressors and inotropes; daily cumulative fluid balances; development of kidney injury; ventilator–free days and alive at day 28 (VFD–28), duration of ICU and hospital stay, and ICU, hospital and 90–day mortality.

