### 5.4.3 Repeated measures

- Within one hour after initiation of ventilation OR within first hour of arrival when the patient has been intubated in another hospital, AND 3 times a day at fixed time points (8:00 AM, and 4:00 PM and 8:00 PM) for a following 3-day period:
  - Ventilation data
    - Ventilation mode;
    - Tidal volume set ( $V_T$ ) (mL);
    - Expiratory tidal volume (VTE);
    - Positive end-expiratory pressure (PEEP) (cm H2O);

- Maximum airway pressure ( $P_{\max}$ ) (cm H2O) or plateau pressure ( $P_{\text{plateau}}$ ) or peak pressure ( $P_{\text{peak}}$ ) (cm H2O);
  - Level of pressure support above PEEP (cm H2O);
  - Inspired fraction of oxygen ( $\text{FiO}_2$ ) (%);
  - Set measured respiratory rate (RR) (min);
  - Inspiration to expiration ratio (I:E) (ratio);
  - Saturation of peripheral oxygen ( $\text{SpO}_2$ ) (%); and
  - End-tidal carbondioxide ( $\text{ETCO}_2$ ) (kPa).
- Arterial blood gas (ABG) analysis
  - pH;
  - Partial pressure of oxygen ( $\text{PaO}_2$ ) (kPa or mmHg);
  - Partial pressure of carbon dioxide ( $\text{PaCO}_2$ ) (kPa or mm Hg);
  - Bicarbonate ( $\text{HCO}_3^-$ ) (mmol/L);
  - Arterial saturation of oxygen ( $\text{SaO}_2$ ) (%);
  - Arterial lactate levels (mmol/L);
  - $\text{FiO}_2$  (%) at time point of ABG; and
  - Position of patient in which ABG was taken.
- Hemodynamics
  - Mean arterial pressure (mmHg);
  - Heart rate (bpm);
- 3 times a day at fixed time points (8:00 AM, and 4:00 PM and 8:00 PM) for a following 3-day period:
  - Received paralytic drugs within the previous 8 hours (yes or no).
- Every day at 8:00 AM for 72-hour period after admission
  - Life status (alive or deceased);
  - Location (in ICU, hospital or other facility);
  - Intubation status;
  - Sequential Organ Failure Scores (SOFA);
  - Cumulative dose of sedatives (mg);
  - Cumulative dose of vasopressors (mg);
  - Cumulative fluid balance during last 24 hours (ml);
  - Amount of fluid administered during last 24 hours (ml);
  - Urine output (ml/hour); and

- Plasma creatinine (mmol/L).
- Prone position (yes or no), and if yes, time and duration (hours);
- ABG in supine position;
- Use of recruitment maneuver (yes or no);
- Undergoing veno–venous, veno–arterial or arterio–venous extracorporeal membrane oxygenation (ECMO) (yes or no);
- Pneumothorax (yes or no)

- Follow-up
  - Life status at day 7, day 28 and day 90;

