## 7. STATISTICAL ANALYSIS

Descriptive statistics will be used to describe the study population, and data are expressed in number and relative proportions for categorical variables and median (quartile 25% – quartile 75%) for continuous variables.

As the outcome of this study is urgently needed, data analysis will be done in two sequential steps. The first step includes an analysis of all patients admitted for invasive ventilation in one of the participating ICUs in the first four weeks after admission of the first COVID–19 patients, which was in all centers within the first weeks of March 2020. This part of the analysis focusses on ventilation practices in the first weeks of the pandemic in the Netherlands. This analysis may underestimate the effect of ventilation variables and parameters on outcomes, as many patients will not yet be weaned from the ventilator and remain admitted in the ICU. The second step includes an analysis of all COVID–19 patients admitted during the total 10 weeks PRoVENT COVID will enroll patients, with a complete follow up till day 90. This analysis will provide an answer to the question whether certain ventilator settings, variables and parameters are associated with patient–centered and other important outcomes.

All analyses will be performed using multilevel (patients nested in hospitals), mixed modelling with hospitals as random effect. Ventilatory variables and parameters will be compared among the groups, and absolute differences with the respective 95%–confidence interval (CI) will be calculated as the absolute difference from a mixed–effect linear model considering the hospitals as random effect to account for within–center clustering. Categorical variables will be compared as the risk difference from the same model.

Cumulative distribution plots will be used to demonstrate the cumulative distribution frequency of ventilation variables. Vertical dotted lines will represent the cut–off for each variable and the horizontal dotted lines the respective proportion of patients reaching each cut–off. Cut–offs to form matrices may use widely accepted values for each variable, specifically 8 mL/kg PBW for tidal volume, 10 cm H2O for PEEP, 30 cm H2O for plateau pressure, and 15 cm H2O for ΔP.

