Mixed–effect multivariable logistic or linear regression model will be used to identify factors independently associated with major outcomes, like death and VFD–28. Subanalyses are planned to investigate differences in ventilation practice and outcomes in the following prespecified subgroups: women versus men, and patients categorized by the body mass index.

All analyses will be conducted in R v.3.6.0 and a p value < 0.05 will be considered statistically significant.

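### Ventilation data accrue for up to 72 hours, but the outcome models set no day 0, exposure record or landmark, so deaths and extubations inside the window can bias the associations

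*Combined protocol and SAP*

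**What the plan says.** Exposure data build up over time. The Summary (Methods) has ventilator data "collected from start of invasive ventilation for up to 72 hours". Section 5.4.3 sets the first record at "Within one hour after initiation of ventilation OR within first hour of arrival when the patient has been intubated in another hospital", and later records "3 times a day at fixed time points (8:00 AM, and 4:00 PM and 8:00 PM) for a following 3-day period". The same section also collects "Prone position (yes or no), and if yes, time and duration (hours"), "Use of recruitment maneuver (yes or no") and ECMO status.

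Section 7 says that the second analysis step will answer "whether certain ventilator settings, variables and parameters are associated with" patient outcomes. The stated tool is mixed-effects regression, logistic or linear, to "identify factors independently associated with major outcomes", with death and VFD-28 as the examples. The secondary objective (Section 2.1.2) concerns duration of ventilation, which overlaps the 72-hour window.

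The plan does not state:
- which of the records, or which summary of them, is the exposure;
- the day from which VFD-28, 28-day mortality and 90-day mortality are counted;
- what happens to patients who die or are extubated before 72 hours;
- any landmark, time-dependent covariate or survival model.

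**The concern.** A model with fixed covariates treats each exposure as known when follow-up starts. A therapy first used on day 2 is not known then. The patient had to stay alive and ventilated until day 2 to receive it, so patients who die or are extubated on day 1 fall mostly into the never-exposed group whatever the therapy does.

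A setting averaged over the window has a related but different problem. Every patient has settings from the start, so there is no unexposed group. However, the average covers fewer and earlier readings in patients who die or are extubated soon, so the measurement depends on the outcome.

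The introduction (Section 1.3) presents the study as a first step towards ventilation guidelines. An association produced only by event timing could therefore be read as guidance on practice.

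**Working it through.** The plan states no figure that could be reproduced here: Section 4.4 has no formal sample size calculation, and no event rates are given. The check therefore sets out the record count and then illustrates size and direction.

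**Records per patient.** One first-hour record plus 3 per day for 3 days gives at most 1 + 3 × 3 = 10, and fewer after early death or extubation.

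**Illustration with no true effect.** All inputs are assumptions; none comes from the documents.
- d and e are the proportions who die or are extubated within 72 h, with times uniform over 0 to 3 days; L = 1 - d - e.
- The therapy starts at a rate of 0.25 per day while the patient is ventilated, independently of outcome.
- Later mortality among those still ventilated at 72 h is 30%.
- VFD-28 is 0 if the patient dies. Late survivors are extubated uniformly over days 3 to 28 (mean VFD 12.5).

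Chance of ever being exposed within 72 h:
- still ventilated at 72 h: pL = 1 - exp(-0.75) = 0.5276
- early death or extubation: pE = 1 - 0.5276/0.75 = 0.2965

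Then:
- P(exposed) = (d + e)·pE + L·pL
- death risk if exposed = (d·pE + 0.30·L·pL) / P(exposed)
- death risk if unexposed = (d·(1 - pE) + 0.30·L·(1 - pL)) / (1 - P(exposed))

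*Early deaths only, d = 10%, e = 0.* P(exposed) = 0.10 × 0.2965 + 0.90 × 0.5276 = 0.5045. Exposed: (0.0297 + 0.1425)/0.5045 = 0.341. Unexposed: (0.0704 + 0.1275)/0.4955 = 0.399. Odds ratio = (0.341/0.659)/(0.399/0.601) = 0.78. VFD-28: exposed 0.63 × 0.5276 × 12.5/0.5045 = 8.24; unexposed 0.63 × 0.4724 × 12.5/0.4955 = 7.51; difference about +0.7 days.

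*Early extubations only, d = 0, e = 10%.* Exposed: 0.1425/0.5045 = 0.282. Unexposed: 0.1275/0.4955 = 0.257. Odds ratio = 1.14 (1.135 before rounding).

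A simulation of 2,000,000 patients per scenario gave the results below. The formulas agree to within 0.01 on the odds ratio and 0.03 days on VFD-28.

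| Dead / extubated by 72 h | OR for death | VFD-28 difference (days) |
|---|---|---|
| 0% / 0% | 1.00 | +0.02 |
| 3% / 0% | 0.92 | +0.24 |
| 5% / 0% | 0.87 | +0.40 |
| 10% / 0% | 0.78 | +0.71 |
| 3% / 3% | 0.96 | -0.26 |
| 5% / 5% | 0.93 | -0.40 |
| 5% / 10% | 0.98 | -1.08 |
| 10% / 10% | 0.88 | -0.74 |
| 0% / 10% | 1.14 | -1.54 |

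**With the remedies.** Restricting to patients alive and ventilated at 72 h gave odds ratios of 1.00 to 1.01 and VFD-28 differences of -0.02 to +0.02 days. An exposure fixed in hour 1, with all patients kept, gave an odds ratio of 1.00 in every scenario.

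A separate simulation under other assumptions (35% 28-day mortality, 5 to 12% dead and 3 to 8% extubated within 72 h, 30 to 70% of the rest exposed) gave odds ratios of 0.94 down to 0.77, and 1.00 with the landmark.

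Both illustrations concern ever/never therapies. Neither measures the truncation effect on averaged settings.

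**The case against.** A reader might infer that the plan commits to a biased analysis in which rescue therapies look protective. The documents do not support that, for four reasons.

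- **Therapies are not named as predictors.** The Summary lists "use of rescue therapies (including prone positioning") among the endpoints, and Section 5.1.2 places prone positioning and recruitment maneuvers beside mortality. ECMO is only a data item in Section 5.4.3. The secondary objective and hypothesis speak of settings. This stands. But Section 7 gives no list of predictors, and its open reference to factors excludes none of these therapies.
- **A first-hour record exists.** If it is the exposure, patients intubated on site contribute no immortal time. The 72 hours is a collection period and not a stated exposure definition. This also stands, but the plan never commits to that record, and it cannot represent a therapy begun later.
- **No time origin is stated.** That outcomes run from the start of ventilation is an inference. For transferred patients the first record is taken at arrival, and Section 4.3 allows up to 24 hours of earlier ventilation in a non-participating hospital. This makes a rule more necessary.
- **The bias has no fixed sign.** Early deaths push towards apparent benefit and early extubations towards apparent harm. With 5% of each, the same inert therapy looks slightly protective for death (0.93) and harmful for VFD-28 (-0.40 days).

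Immortal time is also the wrong name for what happens to averaged tidal volume, PEEP or FiO2.

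**Conclusion.** The point holds as a conditional one. The plan permits this bias without making it certain. It arises if any exposure defined after the first hour enters the fixed-covariate models for death, VFD-28 or duration of ventilation, and nothing in Section 7 prevents that.

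Under the assumed inputs an inert ever/never therapy showed odds ratios for death from about 0.78 to 1.14 and VFD-28 shifts from about +0.7 to -1.5 days. Those ends come from 10% early deaths alone and 10% early extubations alone; scenarios with both lay between 0.88 and 0.98 for death. The true size depends on early event rates and exposure rates that the documents do not give, and on covariate adjustment and hospital effects that were not modelled.

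The descriptive primary objective is unaffected. The secondary objective and the outcome part of the second analysis step are the parts at risk. The change is worth making because it is cheap and uses data already collected.

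**What to change.** Add four rules to Section 7:

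1. Define day 0 for VFD-28 and for mortality, including for patients transferred while ventilated.
2. Make the first-hour record the main exposure for outcomes counted from day 0.
3. For any exposure defined after hour 1 (72-hour summaries of settings, prone positioning, recruitment maneuvers, ECMO), either analyse patients alive and still ventilated at 72 h with outcomes counted from 72 h, or enter the exposure as time-dependent in a survival model.
4. Report how many patients died and how many were extubated before 72 h.

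The cost is a few sentences and some programming, with no new data. Prone positioning has time and duration, which suits a time-dependent analysis. Recruitment maneuvers and ECMO are listed as yes or no without a clock time, so the landmark is the simpler choice for them.

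The landmark result applies only to patients still ventilated at 72 h, and its count of ventilator-free days differs from the listed VFD-28; the report should say both. For transferred patients the first-hour record may come after ventilation began, so rule 2 depends on how rule 1 treats them.

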### **Study endpoints**

Main ventilator settings (including tidal volume, airway pressures, oxygen fraction and respiratory rate) (primary) and parameters (blood gas results); use of rescue therapies (including prone positioning); use of sedatives, vasopressors and inotropes; daily cumulative fluid balances; development of kidney injury; ventilator–free days and alive at day 28 (VFD–28), duration of ICU and hospital stay, and ICU, hospital and 90–day mortality.

### **Nature and extent of the burden and risks associated with participation, benefit and group relatedness**

Retrospective collection of data regarding ventilation management and major clinical endpoints is without risk for the individual patient.

## 1. INTRODUCTION AND RATIONALE

### 1.1 The coronavirus disease 2019

Coronavirus disease 2019 (COVID–19) is a lower respiratory tract infection caused by the severe acute respiratory coronavirus–2 (SARS–CoV–2), of which the first outbreak was reported in Wuhan, China in the beginning of December, 2019. Since then, it has rapidly spread across the globe, with over 60.000 new cases each day as of late March 2020.

Although most people who are infected by SARS–CoV–2 only develop mild symptoms, an estimated 5% of reported cases are admitted to the intensive care unit (ICU) because of severe hypoxemia and dyspnoea [1]. The majority of these patients have shown to require invasive ventilation, and in this group, the mortality is considerable [2].

### 1.2 Lung protective ventilation

Although invasive ventilation can be a necessary supportive strategy in patients with respiratory failure, it also has the potential to worsen pre-existing lung injury or even initiate it [3]. ‘Ventilator-induced lung injury’ (VILI) is mainly due to overdistension of the lungs, and is associated with a longer duration of ventilation and a higher mortality [4]. Lung protective ventilation, featuring low tidal volume ( $V_T$ ), reduced inspiratory plateau pressure ( $P_{plateau}$ ) [5] and low driving pressure (DP) [6] has been suggested to reduce the risk of mortality and is considered the standard of care ([7-10]. The benefit of high positive end–expiratory pressure (PEEP) remains uncertain, as does the use of recruitment maneuvers. There is evidence that high PEEP with recruitment maneuvers harms patients with ARDS [11]. It is highly uncertain whether high PEEP with recruitment maneuvers benefits COVID–19 patients.

### 1.3 Need for an observational study on ventilator settings

Due to the rapid spread of COVID–19, ICUs worldwide are being overloaded with patients requiring invasive ventilation and healthcare workers are struggling to provide the best care. Approaches in clinical care are already known to vary widely between countries and regions, including the way invasive ventilation is applied [12-15]. It is probable that these variances are amplified by a lack of consensus in treatment due to the novelty of COVID–19. Because invasive ventilation of itself has a strong potential to cause lung damage, these variances could be associated with a difference in patient–centered outcomes, like duration of ventilation and mortality.

Therefore, it is of the utmost importance to observe ventilation strategies that are currently being applied in the treatment of COVID-19 patients. To make haste in this time of crisis, we propose a national, observational, retrospective study that is focused on the inventory of ventilation parameters. This study will form an important first step in creating standard guidelines for invasive ventilation of COVID-19 patients. Implementation of standard guidelines could reduce mortality worldwide.

## **2. OBJECTIVES AND HYPOTHESIS**

### **2.1 Objectives**

#### **2.1.1 Primary objective**

To determine and compare invasive ventilation settings and parameters in COVID–19 patients in intensive care units (ICU) of hospitals in the Netherlands.

#### **2.1.2 Secondary objective**

To determine whether certain ventilation settings have an independent association with duration of ventilation.

### **2.2 Hypothesis**

#### **2.2.1 Primary hypothesis**

There is substantial variation in ventilation practices in COVID–19 patients admitted to the ICU's of hospitals in the Netherlands.

#### **2.2.2 Secondary hypothesis**

Certain ventilation settings impact duration of ventilation.

### **3. STUDY DESIGN**

Multicenter, national, retrospective, observational study in COVID-19 patients with respiratory failure, requiring invasive ventilation in intensive care unit (ICU) settings in hospitals in the Netherlands.

## **4. STUDY POPULATION**

### **4.1 Population (base)**

The data of at least 1,000 consecutively invasively ventilated COVID–19 patients admitted to intensive care units (ICUs) of hospitals in the Netherlands. This study will not be restricted to the ‘formal’ ICUs, as patients may also receive invasive ventilation at other locations within the hospital during the COVID–19 pandemic.

### **4.2 Inclusion criteria**

- COVID–19, confirmed with PCR and/or presence of typical abnormalities on chest computer tomography (CT)
- Suspected COVID–19 infection, with no exclusion of diagnosis
- Having received invasive ventilation

### **4.3 Exclusion criteria**

- Age <18 years
- Already included in the same study in another hospital
- Having had received invasive ventilation > 24 hours in a non–participating hospital

### **4.4 Sample size calculation**

No formal sample size calculation is needed. We expect to capture at least 1,000 patients, but will continue collecting data of new patients for at least 8 weeks.

## 5. METHODS

### 5.1 Study parameters/endpoints

#### 5.1.1 Main study parameters

- Ventilation mode;
- Tidal volume set ( $V_T$ ) (mL);
- Expiratory tidal volume (VTE)
- Positive end-expiratory pressure (PEEP) (cm H2O);
- Maximum airway pressure ( $P_{max}$ ) (cm H2O) or plateau pressure ( $P_{plateau}$ ) or peak pressure ( $P_{peak}$ ) (cm H2O);
- Level of pressure support above PEEP (cm H2O);
- Inspired fraction of oxygen (FiO2) (%);
- Set and measured respiratory rate (RR) (min); and
- Inspiration to expiration ratio (I:E) (ratio).

#### 5.1.2 Secondary study parameters

- Number of ventilation-free days and alive at day 28 (VFD-28);
- Duration of ventilation in survivors;
- Use of prone positioning;
- Use of recruitment maneuvers;
- Incidence of acute kidney injury (AKI);
- Duration of ICU stay;
- Duration of hospital stay;
- ICU mortality;
- Hospital mortality;
- 28-day mortality; and
- 90-day mortality.

### 5.2 Randomisation, blinding and treatment allocation

Not applicable.

### 5.3 Study procedures

Patients will be included by the attending clinician. Participating centers will be visited by researchers to collect data of included patients.

## 5.4 Data collection

### 5.4.1 Demographic data

- Age (age categories);
- Gender (male or female);
- Height (cm);
- Weight (kg);
- Medication (categories); and
- Comorbidities (categories).

